1.3 Preclinical Data

N/A

1.4 Clinical Data to Date

We do not expect any adverse side effects associated with the hormonal manipulations outlined in this protocol for the following reasons: We will be administering estrogen paired with selective estrogen receptor modulators (SERMs) to a subset of women with perimenopausal women. SERMs are synthetic non-steroidal agents that have estrogen agonist and antagonist effects in different tissues, to block the negative effects of estrogen on non-target tissues, including the reproductive organs and cardiovascular system, while allowing estrogen to exert effects on target tissues like the brain, and thus decreasing risk for side effects.

Adverse Events Related to Combined Hormone Replacement and the Results of the Women's Health Initiative (WHI): The WHI study demonstrated that continuous administration of one form of estrogen (conjugated estrogens) in combination with one form of progesterone (medroxyprogesterone acetate) is associated with an increased risk of dementia, heart attacks, stroke, blood clots, and breast cancer. TSECs, the form of estrogen that we use in this study, is administered as a sole agent and, consequently, we do not expect that it will pose the increased risks observed with the chronic combination of the conjugated estrogens and medroxyprogesterone administered in the WHI study. Indeed, while the estrogen alone arm of the WHI trial was shown to be associated with an increased risk of stroke, no increased risk of either heart disease or breast cancer was observed^{55,56}. Estrogens may precipitate migraine headaches, and depression has also been reported to occur with the use of estrogens. In general, considering the dose and duration of treatment that we propose to use in this protocol, the risk of developing such side effects is negligible.

Conjugated Estrogens/Bazdoxifene (Duavee): The first such tissue selective estrogen complex (TSEC) approved by the FDA is Duavee, which combines conjugated estrogens and the SERM bazedoxifene [1]. Bazedoxifene has antiestrogenic effects in the endometrium and breast, protecting against uterine and breast cancer, and estrogenic effects in bone, making it a potent preventive agent and treatment for osteoporosis. Duavee has been shown to alleviate hot flashes and vaginal atrophy and prevent osteoarthritis. The safety of conjugated estrogens/bazedoxifene was evaluated in four Phase 3 clinical trials (sponsored by Wyeth) ranging from 12 weeks to 24 months in duration and enrolling 6,210 postmenopausal women age 40 to 75 years (mean age 55 years). A total of 1,224 patients were treated with DUAVEE and 1,069 patients received placebo. The incidence of all-cause mortality was 0.0% in the DUAVEE group and 0.2% in the placebo group. The incidence of serious adverse reactions was 3.5% in the DUAVEE group and 4.8% in the placebo group, and 7.5% of the DUAVEE group and 10.0% of the placebo group withdrew [1]. The most common adverse reactions leading to discontinuation were hot flashes, upper abdominal pain, and nausea. Other less common adverse reactions included diarrhea, dyspepsia, muscle spasms, neck pain, dizziness and oropharyngeal pain [1]. The incidence of endometrial hyperplasia was less than 1% in both clinical studies examining the effect of Duavee on the endometrium [1, 2, 3, 4]. The SMART study examined safety and efficacy of Duavee and found that women reported low incidences of breast pain and high incidences of cumulative amenorrhea, in addition to relief of vasomotor symptoms [5].

1.5 Dose Rationale and Risk/Benefits

This study will enroll perimenopausal women to undergo TSEC supplementation using their existing infrastructure. Many studies have identified perimenopausal women as being at high risk for mood disorders, especially during the late menopause transition, but only a few studies have systematically assessed this biological vulnerability. The benefits of this study are three-fold: 1) increased knowledge of the neuroendocrine mechanisms underlying both the triggering of and susceptibility to depression in women, 2) improved identification of perimenopausal women for whom hormone replacement therapy is likely to have beneficial neuroregulatory effects, and 3) increased information regarding novel targets for pharmacologic intervention. While there are scientific benefits to this study, the benefit to patients will be minimal. TSEC administration may reduce depressive symptoms in some of the participants, and this information may be helpful to women as they plan their future health care in relation to menopause symptom management.

COVID-19 Risks

Participants may experience the potential risk of COVID-19 transmission during required in-person study visits such as at the Biomedical Research Imaging Center (BRIC) and when in close contact with study team members during blood draws when study staff will need to maintain less than 6ft distance. The study team will be following UNC guidelines and BRIC guidelines to take every possible precaution to protect study participants and their staff. Including virtual video or telephone visits when possible, shortening duration of in-person contact, requiring masks at all times for study staff and participants, maintaining 6ft distance when possible, temperature checks on arrival to BRIC, COVID-19 pre-screening 24 hours in advance of any in-person contact and the day of, frequent cleaning with 90% alcohol or 1:10 bleach solution, cleaning equipment between each participant, handwashing required every hour and before or after contact with any participants. While the study team will be taking every pre-caution possible to participants and the study staff there may still be a risk of COVID-19 transmission due to the possibility of the COVID-19 virus

lingering in enclosed spaces from asymptomatic carriers. However this risk should not be any greater than being in an essential public setting such as a grocery store. If a participant or a member of the study team has had direct or even secondary contact with any suspected or confirmed cases of COVID, the study team will reschedule any upcoming visits until the case is confirmed negative or to quarantine for at least 14 days and monitor symptoms. If a participant or study team member experiences any symptoms of COVID-19 including but not limited to: cough, fever, chest pain, trouble breathing, loss of smell or taste, nausea, abdominal pain, vomiting, etc. participants will be asked to notify the study team immediately, contact their Primary Care Provider and their local COVID-19 hotline to get tested for COVID-19.

2 Study Objectives

The long-term research objectives are to 1) advance our understanding of the effects of ovarian hormones on the female brain and how these effects contribute to the triggering of and susceptibility to mood disorders; and 2) to identify neural and endocrine markers of depression risk, thereby improving our ability to prevent affective illness in women. Our central hypothesis is that the neural reward system is hypoactive in PM-MDD, and the antidepressant effects of a three-week TSEC intervention will be associated with increased activity in the neural reward system, assessed using functional magnetic resonance imaging (fMRI).

Aim 1: Determine the extent to which TSEC reduces anhedonia and other depressive symptoms in PM-MDD. Anhedonia and other depressive symptoms will be assessed at baseline and following 3 weeks of TSEC administration.

Aim 2 (Exploratory): Quantify the effect of TSEC on the neural reward system in PM-MDD. We will use fMRI at baseline and following TSEC treatment in PM-MDD to probe frontostriatal reward circuitry. We also will compare the effects of TSEC and ERT in PM-MDD.

Null hypothesis (H_0): TSEC has no salutary effect on depression.

Alternative hypothesis (H_1): TSEC reduces depression as evidenced by 1) a statistically significant decrease in average MASQ Anhedonia scale score following 3 weeks of treatment, and 2) a clinically significant increase of 1 SD in MASQ Anhedonia scale score.

We will test this hypothesis using a paired t-test of MASQ Anhedonia scores at visit 1 (pre-treatment) and visit 6 (post-treatment).

Aim 2 (Exploratory): Quantify the effect of TSEC on the neural reward system in PM-MDD. We will use fMRI at baseline and following TSEC treatment in PM-MDD to probe frontostriatal reward circuitry. We also will compare the effects of TSEC and ERT in PM-MDD.

Null hypothesis (H_0): TSEC has no meaningful effect on activity of the neural reward circuit in response to rewards.

Alternative hypothesis (H_1): TSEC reduces increases neural responsiveness to reward in the frontostriatal reward circuitry as evidenced by increased activation of the caudate, putamen, and nucleus accumbens in PM-MDD in response to reward following TSEC administration (compared with baseline).

We will test this hypothesis using a paired t-test to compare activity in 3 regions of interest (ROIs)—caudate, putamen, and nucleus accumbens—at the pretreatment and posttreatment scans.

3 Study Design

3.1 General Design

Overview. This is an observational, single-center study using tissue-selective estrogen complex (TSEC) to examine the role of frontostriatal hypoactivity in the pathophysiology of perimenopausal MDD. This study will include 6 study visits that will take place over the course of approximately 6 weeks. Out of those 6 visits, 2 of them will require subjects to come to UNC's campus for their MRI visits at BRIC, while the rest of the appointments will be done virtually through HIPAA compliant Zoom, Webex, or phone when zoom is not available. Five visits will require brief in-person contact for phlebotomy, these very brief points of contact will be performed outside the subject's home when possible (i.e. backyard, back porch, or screened porch). In the context of COVID-19, all participants and staff will complete the appropriate screening as recommended by UNC and BRIC policy prior to any in-person contact. During in person visits participants and the study team will be required to wear masks at all times and maintain 6 feet distance when possible to minimize the possibility of COVID-19 transmission. Perimenopausal MDD women will receive Duavee, a TSEC, for 3 weeks. FMRI sessions will occur at baseline and at the end of the third week of medication administration. The procedures that will take place are outlined in **Table 1** and detailed below.

Table 1. Study Procedures and Timeline

Study Visits	1	2	3	4	5	6
Maximum duration of in-person visit (hours)		1	2	0.15	0.15	2
Consent	X					
OBGYN Exam		X				
fMRI			X			X
PRT			X			X
Venipuncture		X	X	X	X	X
SCID	X					
SNAP	X		X	X	X	X
HAM-D	X		X	X	X	X
IDAS	X		X	X	X	X
GCS	X		X	X	X	X
PSQI			X			X
HHQ						X
THQ						X
Duavee Rx Provided			X	X	X	
Payment	\$100	\$30	\$150	\$35	\$35	\$150

Participants. Participants will include healthy, unmedicated perimenopausal women ages 44-55 with (n=20) current major depression.

Hormone Administration.

Prior to beginning medication, women will have a basic lab panel and serum pregnancy test, pelvic exam, breast exam, and PAP smear. Participants who can provide record of a pelvic exam and breast exam within the past year and normal pap results within the past three years will be permitted to decline the GYN exam. Women will be seen in the clinic each week during medication administration to assess blood levels of estradiol and mood symptoms.

Optional Home Visits: In an effort to increase recruitment and retention, the study team will offer home visits for Study Visits 1, 4, 5, as well as Baseline Labs.

Clinical Assessments

The Structured Clinical Interview for DSM-IV-TR Axis-I Disorders (SCID)⁵⁸ and the Schedule for The SCID1 will be administered at baseline to determine study eligibility. The following standard measures will be administered at baseline, both fMRI sessions, and weekly clinic visits:

- The Positive and Negative Affect Schedule⁵⁹ is a 20-item questionnaire that measures both positive affect (PA) and negative affect (NA) and is sensitive to subtle changes in affect over time.
- The Hamilton Rating Scale for Depression (HRSD)⁶⁰ is a 21-item researcher-rated standardized scale that assesses depressive symptoms and is widely used as a measure of symptom change over time.
- The Inventory of Depression and Anxiety Symptoms (IDAS)⁶¹ is a 64-item self-report questionnaire that comprehensively assesses anxiety and depression symptoms on 10 subscales. The IDAS has excellent psychometric properties and has been validated for assessing reproductive mood disorders.
- The Mood and Anxiety Symptom Questionnaire – Anhedonic Depression Subscale (MASQ-AD)⁶² is a 22-item scale that assesses anhedonia (i.e., loss of interest and low positive affect). MASQ-AD scores have been associated with blunted striatal response to reward in previous studies of patients with depression⁶³.
- The Greene Climacteric Scale (GCS)⁶⁴ is a 21-item scale that is the gold-standard measure of four domains of climacteric symptoms: vasomotor, somatic, anxiety, and depression.
- The Pittsburgh Sleep Quality Index (PSQI)⁶⁵ is a 9-item questionnaire that measures the quality and sleep patterns in older adults. *This measure will only be administered at the two fMRI sessions.
- The Hormone History Questionnaire is a 19-item inventory that assesses women's mental and physical health and was created for the purpose of this study.
- The Trauma History Questionnaire¹⁴ is a 24-item measure that examines participant's experiences with potentially serious or traumatic life events.

While the SCID and HAM-D are researcher administered, the other measures will be collected through self-report questionnaires using Qualtrics or paper and pencil questionnaires.

Despite the use of exclusion criteria designed to reduce risk to participants, depressive symptoms are monitored closely. Any subject who develops severe depressive symptoms (e.g., suicidal ideation) will be discontinued from the study and offered treatment paid for by the study. If inpatient hospitalization becomes necessary as a result of the study, UNC Health Care will cover the cost. The following language has been added to the study consent form to reflect this policy:

"All research involves a chance that something bad might happen to you. This may include the risk of personal injury. In spite of all safety measures, you might develop a reaction or injury from being in this study.

"If you become depressed or anxious as a direct result of participating this study, the UNC Department of Psychiatry will provide outpatient medical treatment. If vaginal bleeding or any other gynecological problem occurs, we will arrange for a visit with a UNC gynecologist. The research study will cover the costs of such outpatient exams and treatment at UNC Health Care.

"If you become sick or injured as a direct result of participating in this study, and your condition cannot be addressed with outpatient treatment, UNC Health Care will provide all needed inpatient medical treatment. UNC Health Care will reimburse you for reasonable and necessary costs of such inpatient medical treatment not covered by your insurance company. No other form of reimbursement for study-related injury or illness is offered by UNC Health Care. You do not give up any legal rights by signing this consent.

"If you receive Medicare benefits, UNC Health Care is required by law to report payments made to you for treatment, complications, and injuries that arise from this study. Information that you are taking part in this study, medical treatments received, Medicare claims, and other personal information about your such as your name, social security number, and date of birth, will be provided to the Centers of Medicare and Medicaid Services and its agents and/or contractors for this purpose.

"If you seek treatment outside of UNC Health Care, you will be responsible for the costs of your treatment."

FMRI Tasks

The following task will be included in each of the two fMRI sessions:

The Monetary Incentive Delay (MID) Task⁶⁶ engages the reward circuitry during monetary incentive anticipation and outcomes. Each of two MID runs consists of 90 6-second trials during which subjects are presented with one of nine cue shapes, a fixation crosshair (for a variable duration), the target, and performance (win/loss/neutral) feedback. The cue indicates whether it is an incentive (gain, loss) or non-incentive trial. During incentive trials, participants can either gain or lose money by pressing a button during target presentation. Task difficulty is based on participant reaction times. This task elicits reliable frontostriatal dysregulation in people with remitted MDD⁶⁷. Resting state scans will also be conducted at the beginning and end of each session.

FMRI Data Acquisition and Image Processing

Scanning is performed using a Siemens Magnetom 7T TIM Trio scanner. High-resolution, T1-weighted anatomical images will be acquired using an MPRAGE sequence. Whole-brain functional images will be acquired using a single-shot, gradient recalled echoplanar pulse sequence sensitive to blood-oxygen-level-dependent (BOLD) contrast. Each of 2 runs will consist of the acquisition of 195 successive brain volumes. fMRI image preprocessing, processing, and analysis will be conducted using FSL and custom MATLAB scripts. fMRI analyses will include an event-related BOLD response analysis within *a priori* structurally defined frontostriatal regions of interest (ROIs). Contrasts of interest will include win versus non-win outcomes⁶⁸, although the anticipation of wins will also be explored.

Other Tasks

Probabilistic Reward Task (PRT)⁶⁹ will be conducted outside of the scanner. This task allows us to test the additional hypothesis that perimenopausal depression is characterized by blunted reward learning. During this task, correct identifications of two ambiguous stimuli are differentially rewarded. The task will consist of 300 trials, divided into 3 blocks of 100 trials. Each trial starts with the presentation of a fixation cross for 500 msec followed by a mouthless face. After a delay of 500 msec, either a short mouth (11.5 mm) or a long mouth (13 mm) is presented for 100 msec. Participants will be asked to identify which type of mouth was presented. For each block, the long and short mouths are presented equally often in a pseudorandomized sequence and 40 correct trials are followed by reward feedback immediately after the correct response. An asymmetrical reinforcer ratio will be used in this task, such that for half of the participants, correct identification of the short mouth will be associated with three times more positive feedback (30 of 40) than correct identification of the long mouth (10 of 40). For the other half of the participants, the contingencies will be reversed.

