- The Inventory of Depression and Anxiety Symptoms (IDAS)⁶¹ is a 64-item self-report questionnaire that comprehensively assesses anxiety and depression symptoms on 10 subscales. The IDAS has excellent psychometric properties and has been validated for assessing reproductive mood disorders.
- The Mood and Anxiety Symptom Questionnaire – Anhedonic Depression Subscale (MASQ-AD)⁶² is a 22-item scale that assesses anhedonia (i.e., loss of interest and low positive affect). MASQ-AD scores have been associated with blunted striatal response to reward in previous studies of patients with depression⁶³.
- The Greene Climacteric Scale (GCS)⁶⁴ is a 21-item scale that is the gold-standard measure of four domains of climacteric symptoms: vasomotor, somatic, anxiety, and depression.
- The Pittsburgh Sleep Quality Index (PSQI)⁶⁵ is a 9-item questionnaire that measures the quality and sleep patterns in older adults. *This measure will only be administered at the two fMRI sessions.
- The Hormone History Questionnaire is a 19-item inventory that assesses women's mental and physical health and was created for the purpose of this study.
- The Trauma History Questionnaire¹⁴ is a 24-item measure that examines participant's experiences with potentially serious or traumatic life events.

While the SCID and HAM-D are researcher administered, the other measures will be collected through self-report questionnaires using *Qualtrics* or paper and pencil questionnaires.

Despite the use of exclusion criteria designed to reduce risk to participants, depressive symptoms are monitored closely. Any subject who develops severe depressive symptoms (e.g., suicidal ideation) will be discontinued from the study and offered treatment, including inpatient hospitalization.

FMRI Tasks

The following task will be included in each of the two fMRI sessions:

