8.3.5 Sponsor reporting: *Notifying participating investigators*

N/A

8.4 *Unblinding Procedures*

N/A

8.5 *Stopping Rules*

The protocol only includes rules for discontinuing individual participant, but not rules for stopping the entire study:

Adverse mood symptoms will be monitored by administering the Hamilton Rating Scale for Depression (HRSD) at each study visit. If suicidal thoughts or severe mood symptoms are observed at any period in the protocol, then the HRSD will be administered on consecutive days for three days. Anyone scoring > 20 on the HRSD or expressing concerns about their ability to continue in the study, will be considered to have severe mood symptoms and be discontinued from the protocol. In the event of the occurrence of severe mood symptoms, the protocol will be terminated. Should this step prove to be unsuccessful, conventional medication will be prescribed as needed. Further, although we do not anticipate severe adverse reactions, we have arranged for inpatient hospital admission in the Psychiatry Department if symptoms are otherwise unmanageable.

8.6 *Medical Monitoring*

The principal investigator will oversee the safety of the study at her site. This safety monitoring will include careful assessment and appropriate reporting of adverse events as noted above, as well as the construction

and implementation of a site data and safety-monitoring plan. Medical monitoring will include a regular assessment of the number and type of serious adverse events.

The Principal Investigator's responsibilities are to:

- review the research protocol, informed consent documents, and plans for data safety and monitoring;
- evaluate the progress of the trial, including periodic assessments of data quality and timeliness, participant recruitment, accrual and retention, participant risk versus benefit, performance of the trial site, and other factors that can affect study outcome;
- consider factors external to the study when relevant information becomes available, such as scientific or therapeutic developments that may have an impact on the safety of the participants or the ethics of the trial;
- protect the safety of the study participants;
- report on the safety and progress of the trial;
- make recommendations to the UNC-CH IRB, and the PI, concerning continuation, termination, or other modifications of the trial based on the observed beneficial or adverse effects of the treatment under study;

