- if appropriate, conduct interim analysis of efficacy in accordance with stopping rules which are clearly defined in advance of data analysis;
- ensure the confidentiality of the trial data and the results of monitoring; and,
- assist the UNC-CH IRB by commenting on any problems with study conduct, enrollment, and sample size and/or data collection.

The principal investigator or one of her trained study staff will be present at all visits to assess psychological changes using interviews and scales (i.e. HDRS, SCID, IDAS). If the subject self-reports suicidal ideation, this will be immediately communicated to the principal investigator, who will assess each subject on a case-to-case basis.

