ACOG Practice Bulletin No. 141: management of menopausal symptoms. (2014). *Obstetrics and Gynecology*, 123(1), 202–216.

B. Adherence statement

The Data and Safety Monitoring Plan (DSMP) outlined below will adhere to the protocol approved by the University of North Carolina at Chapel Hill IRB.

II. Adverse Events

A. Adverse event assessment

This study defines adverse event as any unfavorable and unintended sign, symptom, or disease temporally associated with the subject's participation.

The estimated level of risk to subjects for this protocol is level 2: minor increase over minimal risk.

Potential Risks to Human Subjects and Minimization of those Risks

Psychological Assessment

Clinical interviews and self-report assessments contain questions regarding sensitive personal information. As a result, participants may become upset or embarrassed when discussing current or past distressing life events. This risk is necessary in order to assess depressive symptoms and associated psychopathology. However, we have conducted several studies assessing depressive symptoms in women, and participants are unlikely to become upset. If participants become upset during an assessment, they will be reminded of their right to discontinue participation, suicidal ideation will be assessed, and appropriate treatment referrals will be provided. Participants in need of medical follow-up or psychological counseling will be referred to the UNC Psychiatry Outpatient Clinic. If a participant reports having suicidal thoughts, intent, plans, and means during the course of the study, she will be taken to the UNC Emergency Department for evaluation.

MRI

The psychological risks associated with the MRI include the discomfort some subjects encounter by the confinement within the bore of the MRI system (i.e., claustrophobia) and the loud noise made by the gradients during imaging. These risks occur for all clinical MRI exams and are not increased by the proposed research. Nonetheless, the steps taken to reduce these risks are described below.

Claustrophobia

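### Two discontinuation texts conflict for a woman with new suicidal thoughts on study, an HRSD of 20 or less and no voiced concern: one requires stopping, the other does not

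*Combined protocol and SAP*

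**What the plan says.** Two texts say when suicidal thoughts lead to discontinuation.

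**Text A** (3.1 General Design, Clinical Assessments): "Any subject who develops severe depressive symptoms (e.g., suicidal ideation) will be discontinued from the study and offered treatment paid for by the study". Section 6, Clinical Assessments, repeats it with a different ending: "Any subject who develops severe depressive symptoms (e.g., suicidal ideation) will be discontinued from the study and offered treatment, including inpatient hospitalization".

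**Text B** (8.5 Stopping Rules; essentially the same wording in 4.4.1 and in Appendix A, Stopping Rules—Individual Subject) calls for three daily ratings: "If suicidal thoughts or severe mood symptoms are observed at any period in the protocol, then the HRSD will be administered on consecutive days". The criterion follows: "Anyone scoring > 20 on the HRSD or expressing concerns about their ability to continue in the study" is classed as having severe mood symptoms and is discontinued.

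Two further steps appear elsewhere.

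- Section 8.6, Medical Monitoring: "If the subject self-reports suicidal ideation, this will be immediately communicated to the principal investigator, who will assess each subject on a case-to-case basis".
- Appendix A, under Psychological Assessment, covers a participant who "reports having suicidal thoughts, intent, plans, and means during the course of the study, she will be taken to the UNC Emergency Department for evaluation".

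These other provisions bear on the point:

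- Current suicidal ideation is an entry exclusion (4.2, item 26).
- A woman who leaves the hormone protocol is asked to continue self-report ratings but has no further fMRI (4.4.2).
- Only protocol-compliant participants are analysed (7.3).
- Section 8.5 says the protocol has rules for discontinuing individuals and none for stopping the study. Section 3.4 lists primary safety endpoints as not applicable.

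**The concern.** Text A treats suicidal ideation as sufficient in itself to end participation. Text B treats it as a reason to measure, and lets the HRSD score or the woman's own concern decide. Staff following Section 3.1 or 6 and staff following 4.4.1 or 8.5 could handle the same woman differently, each in line with the protocol.

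The first thing at stake is safety. All participants have current major depression, and these texts are part of the only stopping rule the trial has.

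The second is the data. Discontinuing the hormone protocol removes the post-treatment scan, and may take the woman out of the analysis set. Inclusion would then depend on which section was consulted.

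**Working it through.** No figure in the plan depends on this point, so the check is a comparison of texts.

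**Step 1: does Text A apply to ideation seen on study?** Text A concerns a subject who develops such symptoms. Current ideation is excluded at entry (4.2, item 26), so ideation observed later is newly developed and falls within Text A. The documents use suicidal ideation and suicidal thoughts without distinguishing them, and I read them as the same thing.

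**Step 2: apply each text to each case.**

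| New suicidal thoughts, and | Text A (3.1, 6) | Text B (4.4.1, 8.5, Appendix A) | Conflict |
|---|---|---|---|
| HRSD above 20 | Discontinue | Discontinue | Timing only |
| HRSD 20 or less, concern voiced | Discontinue | Discontinue | Timing only |
| HRSD 20 or less on all three days, no concern voiced | Discontinue | Not required | Opposite outcome |

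As an illustration, take a woman at visit 4 with new suicidal thoughts, a total of 15 on each of the three days and no concern about continuing. Text A ends her participation. Text B contains nothing that does.

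**Step 3: does any section settle the third row?**

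- Section 8.6 requires immediate notice to the principal investigator and an individual assessment. It mentions neither Text A nor Text B.
- The Emergency Department sentence needs thoughts together with intent, plans and means. It orders an evaluation and is silent on participation.
- No section ranks the texts or cross-refers between them.

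**Step 4: which rating counts?** Text B calls for three daily ratings but does not say whether one total above 20 is enough or whether a particular day decides. The sentence can be read as covering any score, but that is not stated.

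**Step 5: size.** One woman is 1/20 = 5% of the planned sample. The documents give no rate of new ideation, so the expected number in the third row cannot be derived.

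For context only, take a paired t-test with standardised effect d = 0.7 (7.1) and an assumed two-sided alpha of 0.05, since the plan states neither alpha nor sidedness. Power comes from the noncentral t distribution with n − 1 degrees of freedom and noncentrality d√n. It is about 84% at n = 20, 82% at n = 19 and 80% at n = 18. The plan states 80% for n = 20, so losing one or two women would not by itself undo that figure. The contradiction does not rest on power.

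**The case against.** The best defence is that the texts form a sequence. Sections 3.1 and 6 state the principle, 4.4.1 and 8.5 supply the procedure, and 8.6 puts every report of ideation before the principal investigator at once. Section 4.4.1 also places withdrawal decisions under the principal investigator, co-investigators and research coordinators. This may be what was intended, but the wording does not carry it. Text A allows no intermediate step that could end without discontinuation, and it names ideation itself as an example of a severe symptom. It does not adopt a score above 20 as the definition. Investigator discretion cannot be squared with a mandatory stop unless the protocol says which prevails.

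Other parts of the defence stand, and they rule out several stronger readings:

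- A reader might count four competing rules. The Emergency Department step is not a rule about staying or leaving and is compatible with the rest. Section 8.6 is an assessment step that does not say anyone is retained. The discontinuation conflict is between two texts, each repeated.
- A reader might say Text B stops a woman only above 20. Voiced concern is a second, independent trigger. Text B is also silent on a woman who meets neither; it does not say that she continues.
- A reader might infer that the conflict decides whether the woman with the worst mood is scanned. A woman scoring above 20 is discontinued under both texts, so the disputed case lies at 20 or below.
- A reader might infer that an at-risk woman simply waits three days for a score. Section 8.6 requires immediate notice to the principal investigator.
- A reader might infer that visits 4 and 5 are wholly remote, so the Emergency Department step could not be carried out. Section 3.1 schedules brief in-person blood draws at those visits and offers them as home visits.

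**Conclusion.** The contradiction is real and narrow. The plan is wrong as written for a woman with new suicidal thoughts, HRSD totals of 20 or less and no voiced concern: Sections 3.1 and 6 require discontinuation, while 4.4.1, 8.5 and Appendix A do not. In the remaining cases the two texts differ only in timing. The steps in 8.6 and in the Psychological Assessment part of Appendix A are separate and linked to neither text.

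The conclusion assumes that ideation and thoughts mean the same thing. The effect on scans follows if discontinuation under either text includes the hormone protocol (4.4.2). The effect on the analysis set depends on whether a discontinued woman counts as protocol-compliant under 7.3, which does not define the term. She may still supply self-report scores under 4.4.2, so those data need not be missing even if they go unanalysed.

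The point warrants correction because it sits in the trial's only stopping rule, although the affected group may be small or empty. Which rule is clinically right is not something this review addresses.

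**What to change.** Reconcile the texts in 3.1, 4.4.1, 6, 8.5 and the Stopping Rules part of Appendix A into one rule. State it once in 4.4.1 and replace the other versions with cross-references. The rule should say:

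1. whether suicidal ideation alone ends participation, or whether only the HRSD score or voiced concern does;
2. which of the repeated HRSD ratings counts;
3. how the investigator assessment in 8.6 and the Emergency Department evaluation in Appendix A fit with it.

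The investigators and the IRB choose the content; no clinical rule is proposed here. The cost is a wording amendment, with no added visits, staff or procedures.
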